 5. Subjects who satisfactorily complete above tasks including the 4 scheduled GCRC visits will have a pregnancy test and, if not pregnant, will be given a mammography, a bilateral breast MRI, and duplicate DEXA bone density tests (L2 to L4 and hip) during one of these GCRC visits. The mammogram results will be interpreted immediately as for all clinical mammography tests by a licensed radiologist. Dr. [name] (certified to interpret mammograms and breast MRI), our co-investigator will interpret the mammograms and if there are abnormalities, the subjects will be informed the test results by phone and by mail by the Radiology Staff according to the established clinical protocol in place in our Radiology Department. Specifically, the subjects will be advised to have additional diagnostic tests and be advised to consult their own physician for this follow-up. The cost of these follow-up diagnostic tests will not be the responsibility of this project. If the subjects have cancer lesions after further diagnostic tests, they will be excluded from the study. [name] will inform [name] and the PI of any abnormal test results. PI will also phone

- study subject, advise the subject to consult her personal physician, to have follow-up diagnostic tests, and to inform us the results of the diagnostic tests to determine their continuing eligibility in our study. [name] will also assess the density of these women according to the established diagnostic guideline. [name] who is certified to interpret DEXA results will interpret bone density results for this project.
6. Pregnancy test will be determined during screening and during pill intervention if menstrual cycle lengthens by 2 weeks or more, or within 48 hours prior to scheduled mammography and DEXA bone density tests.

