 13. After completing 12 months of pill supplement, subjects will complete another Harvard DAQ (recall food intake frequency for the past 12 months of pill intervention) and will be given a pregnancy test, followed by a mammography, a breast MRI, and a DEXA bone density test.

14. Subjects will continue consumption of the assigned pill, have the 1-day visit to GCRC for blood draw and other study procedures once every three months (e.g. repeat steps 6 to 14) for another 12 months.
15. Pregnancy test will be performed whenever cycle length increases by >30% of each subject's usual length. Pregnancy test will also be performed no longer than 48 hrs prior to taking mammography and DEXA tests to ensure that pregnant women are not exposed to radiation. Gynecological examination including Pap smear will be done at the end of the study.
16. Transvaginal probe ultrasonography and endometrial biopsies will be performed when medically indicated, for example, if amenorrhea develops. This will be performed by Dr. [name].

Risk and Benefit Assessment:

The soy isoflavone are currently available as pills over-the-counter and are found in soy foods sold to the public. We will use isoflavone tablets provided by the Archer Daniel Midland Co., which we have used in the past several years for several preliminary studies. These isoflavones are isolated by repeated alcohol extractions of soy protein isolates or soy protein concentrates (different processing). Alcohol is then removed by evaporation and the residues used for tablet formulation. In this way, the make-up of the isoflavones is the same as that which exists naturally in soy. These pills are sold as nutritional products over-the-counter to the public. The placebo pills contain maltodextrin, a carbohydrate, and should have no biological effect at the dose, 150 mg, to be given to the subjects.

Populations consuming soy have reduced risk of breast and endometrial cancers, reduced mammographic density, and reduced hip fracture rate. The FDA has approved a health claim regarding soy consumption and risk reduction for cardiovascular diseases. There are no other known risks from soy isoflavones from population-based studies, as soy products are commonly consumed in many countries. However, adverse effects have not been previously looked for carefully, so it is possible that there are unknown risks.

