Lowering of female hormones due to prolonged soy isoflavone ingestion may lower bone density, which could increase the risk of eventually developing osteoporosis (thin bones) and bone fractures. But this is not a known risk. Soy isoflavones have been shown to improve bone mineral density in animals. Asian populations consuming high levels of soy have lower rates of hip fracture compared to western countries. Because the current available information does not allow us to estimate the benefit and the risk of soy consumption on bone density, observations about bone is a part of this study. The risk of osteoporosis might also be increased if subject's calcium intake is not sufficient during the study. Subjects will be advised to adjust their calcium intake if needed to maintain an adequate intake.

Potential adverse effects such as lengthening of the menstrual cycle and nipple fluid cytology will be looked for closely during this study. If menstrual cycle lengths increase by more than 2 weeks in 12% of the participants (e.g. 12 subjects) for more than 3 cycles, the pill assignment codes for these women will be examined to assess if this is intervention-related. If this is associated with treatment, the ovarian hormones of these subjects will be immediately analyzed. The luteal progesterone levels in these women should be less than 1 ng/ml. If cycle length increase persists in these women for longer than 3 months, breast density in these women will be assessed first by breast MRI (because this involves no radiation exposure) and is likely to show changes. The pill supplement will be terminated in these women, but will be continued in the remaining study subjects. If cycle lengths increase in more than 30% of participants and this increase is study related, the pill intervention will be terminated and end of study mammography, bone density test by DEXA, and breast MRI will be performed.

If women develop amenorrhea, transvaginal probe ultrasonography and endometrial biopsies will be performed to ensure no adverse effects on the uterus. [name]. (a co-investigator) will prescribe and perform these tests. Study subject will be provided with a written pathological report for consultation with subject's own primary physician. Reports will also be provided to the Medical Monitor.

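### The only written pill stop for a woman with persistent cycle lengthening waits for a group count and a code check, and the count contradicts itself (12% of 200 is 24, not 12)

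*Combined protocol and SAP*

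**What the plan says.** **Cycle lengthening.** Risk and Benefit Assessment opens its rule with a group trigger: "If menstrual cycle lengths increase by more than 2 weeks in 12% of the participants (e.g. 12 subjects) for more than 3 cycles", the codes of the affected women are examined. If the lengthening is associated with treatment, their ovarian hormones are analyzed. If it goes on for longer than three months, they have a breast MRI, and "The pill supplement will be terminated in these women, but will be continued in the remaining study subjects". A second group rule covers the whole trial: "If cycle lengths increase in more than 30% of participants and this increase is study related, the pill intervention will be terminated".

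**Below the trigger.** The required action for one woman is a pregnancy test. Clinical Procedures item 6 asks for it "during pill intervention if menstrual cycle lengthens by 2 weeks or more". Item 15 says "Pregnancy test will be performed whenever cycle length increases by >30" percent of her usual length.

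**Individual definition.** Reporting of Serious and Unexpected Adverse Events already defines persistent lengthening for a single woman: over two weeks per cycle, not pregnant, over three cycles. It lists this and amenorrhea as expected events.

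**Amenorrhea.** The work-up is individual: "If women develop amenorrhea, transvaginal probe ultrasonography and endometrial biopsies will be performed to ensure no adverse effects on the uterus", and "Reports will also be provided to the Medical Monitor". Item 16 is softer: "Transvaginal probe ultrasonography and endometrial biopsies will be performed when medically indicated, for example, if amenorrhea develops". The paragraph before Statistical Analysis adds a group rule. Above 6% of subjects, given as 12, codes are broken for these women, and the study ends if the amenorrhea is related to isoflavones.

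**The concern.** In the lengthening rule, the women whose pills are stopped are the women counted at the trigger. Whether the first affected woman reaches a mandatory stop therefore depends on how many others are affected and on opening codes. Neither is needed for a clinical decision about one woman, which a blinded physician can make. The protocol itself expects luteal progesterone below 1 ng/ml in the treatment-associated group, against an entry requirement above 8 ng/ml, and it names lower bone density as a possible, though not known, consequence of lowered hormones.

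The trigger also has two values. Staff applying the percentage would wait for twice as many women as staff applying the count. For amenorrhea the work-up is individual, but the available text does not say whether the woman goes on taking pills meanwhile.

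**Working it through.** **Inputs from the protocol.** 200 women, 100 per arm (Abstract; Study Population); lengthening trigger 12%, or 12 subjects; whole-intervention stop above 30%; amenorrhea trigger above 6%, or 12 subjects; 24 months of pills.

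**1. Reproducing the stated count.**
- 0.12 × 200 = 24, not 12.
- 12 / 200 = 6%. The amenorrhea rule reproduces on this base: 0.06 × 200 = 12.
- 0.12 × 100 = 12, so the stated pair fits only one arm. But the text refers to participants, and codes are opened only after the trigger, so blinded staff could not apply a per-arm count.
- 0.30 × 200 = 60, so the whole-intervention stop needs more than 60 women.

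The base of 200 is not firm. Power analysis and sample size justification recruits until 200 women complete at least 1.5 years. At its 15% attrition that is about 200 / 0.85 = 235 women, and 12% of 235 is about 28. That does not bring the percentage and the count together.

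**2. How much the reading matters (illustration).** The protocol gives no event rates, so all rates here are assumptions. Let the number of women ever meeting the definition be X = Binomial(100, p1) + Binomial(100, p0), with p1 for isoflavones, p0 for placebo and no dropout.

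| p1 | P(X ≥ 12), p0 = 1% (range for p0 = 0 to 2%) | P(X ≥ 24), p0 = 1% (range for p0 = 0 to 2%) |
|---|---|---|
| 5% | 0.018 (0.004–0.050) | 0.0000 (0.0000–0.0000) |
| 10% | 0.421 (0.297–0.544) | 0.0002 (0.0000–0.0008) |
| 15% | 0.891 (0.837–0.930) | 0.026 (0.012–0.050) |
| 20% | 0.993 (0.987–0.996) | 0.267 (0.189–0.354) |

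These are chances that the count is ever reached, not chances of harm.

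**3. Time for one woman to meet the definition.** More than three cycles means at least four, each over 14 days longer than usual. For assumed usual cycles of 25, 28 and 35 days:
- 4 × (25 + 14) = 156 days, 5.1 months
- 4 × (28 + 14) = 168 days, 5.5 months
- 4 × (35 + 14) = 196 days, 6.4 months

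These are lower bounds. If the three months of persistence come on top, the times are 8.1, 8.5 and 9.4 of the 24 months. The text does not say whether the two periods overlap.

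**4. Comparison within the protocol.** For allergy-like symptoms, Risk and Benefit Assessment writes a rule for one woman: pause, resume, and discontinue if symptoms recur. It needs no group count and no code break.

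**The case against.** **Earlier stopping is not forbidden.** A reader might infer that the protocol keeps an early-affected woman on pills until enough others join her. The documents do not support that. The rule sets a point at which stopping becomes mandatory. Before it, a woman may withdraw at any time (Recruitment). The consent visit warns of removal after certain test results, with low progesterone as an example. Medical changes found at visits may affect continuing eligibility (Clinical Procedures). Remuneration allows removal for serious unexpected conditions, although its reach is arguable for events listed as expected. Aggregate reports on recurring adverse events can lead to protocol modification or study termination without any 12% count. All of this stands: what is missing is a required decision, not permission to make one. The proposed decision also leaves clinical judgment open, but it would be required, recorded and made without codes.

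**Amenorrhea is not unprotected.** The individual work-up, the report to the Medical Monitor and the study-level stop are all written. Only the pill decision that goes with the work-up is absent from the text seen, which is closer to missing detail.

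**Some text was not available.** It breaks off in the personnel-roles section after the principal investigator's entry, and the duties of the physician and the Medical Monitor may follow there. This limits any statement that something is absent. It does not touch the contradictory threshold or the group wording, which stand in the text seen.

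**The rates are invented.** This is true, and the Introduction reports no amenorrhea in the investigators' earlier studies. The table shows sensitivity to the reading and predicts nothing.

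**Stopping pills costs information.** This also stands. The protocol expects density change in the affected women, so stopping them removes exposure from likely responders.

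**Conclusion.** The concern holds in a limited form. In the available text, the only written pill stop for a woman with persistent lengthening follows a group threshold, a code check for association with treatment, and persistence beyond three months; anything earlier is discretionary. The threshold is wrong as written: on 200 participants, 12% is 24 and 12 is 6%. That arithmetic needs no assumption beyond the planned sample size. Under assumed rates, the choice between 12 and 24 can largely decide whether the mandatory stop is ever reached: 0.89 against 0.03 at 15% on isoflavones and 1% on placebo. At 5% neither count is likely to be reached.

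A reader might go further and infer that women would be harmed. The documents give no event rates and no evidence of harm, so that does not follow. The point should be corrected because it concerns a safety threshold and the correction is cheap. Confidence is medium because part of the text was not available.

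**What to change.** 1. State one lengthening threshold on the pooled, blinded count: either 12 of 200 (6%, matching the amenorrhea rule) or 24 of 200 (12%). Do not use a per-arm count. Say whether the rule acts on reaching the number or on exceeding it, since the amenorrhea rule uses the latter.
2. Detach the individual pill decision from the group count and the code break. The co-investigator physician, with the Medical Monitor, makes and records a blinded hold-or-stop decision for each woman who meets the definition under Reporting of Serious and Unexpected Adverse Events. The same decision is made alongside the existing work-up for each woman with amenorrhea. The clinical criteria are for the investigators and the Medical Monitor to set.
3. Keep group counts and code breaks for study-level decisions. Keep women who stop pills in follow-up and in the intent-to-treat analysis.

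**Cost.** This is a wording amendment using staff already in the protocol. At assumed rates of 10% on isoflavones and 1% on placebo, it means about 10 + 1 = 11 lengthening decisions over the study. Some extra women would stop pills, possibly unequally by arm and among those expected to show density change. That would dilute the treatment contrast by an amount not computed here.

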Reporting of Serious and Unexpected Adverse Events:

Adverse experiences that are both serious and unexpected will be immediately reported by telephone within 24 hr and in writing within 3 days to: 1) UTMB IRB, 2) UTMB GCRC, and 3) UTMB Research Subject Advocate.

A UTMB IRB Adverse Event Report form will be used to report individual serious adverse event. For recurring adverse event, an aggregate report form will be generated to provide summary statistics for the study that will include resolution and potential protocol modification or study termination. The adverse event reports will include the name of P.I. ([name].) and co-investigators ([name]., [name]., and [name].), name of the study (Mammographic Density and Soy Isoflavones), UTMB IRB number (03-260) and UTMB GCRC protocol number (#635), the number of subjects enrolled to date, the number and type of serious and unexpected adverse events previously reported. The report of the medical monitor ([name]) and a follow-up report describing the resolution of the adverse event will also be provided.

The expected adverse events are lengthening of menstrual cycle by more than 2 weeks per cycle in the absence of pregnancy for more than 3 cycles, amenorrhea, unexpected vaginal bleeding, breast lumps, abnormal endometrial histology/cytology, abnormal nipple aspirate cytology, and abnormal blood chemistries. Unanticipated adverse events are breast cancer, ovarian cancer, uterine cancer, intercurrent illness and intercurrent injuries. Serious adverse events are life threatening drug interaction, death, breach of confidentiality, and hospital admission.

Disposition of Data: All notebooks, Harvard DAQ, data collection forms, signed copies of the informed consent, and PHQF relating to this study will be kept in the locked filing cabinets on the [name], Division of Human Nutrition, Department of Preventive Medicine and Community Health, [name] where PI's office is located. The electronic data will be stored on the UTMB PMCH server (pmch on utmbf4) and the Bioinformatics Core facility of GCRC until published, and then archived in CD ROMs at the end of the study. The records will be kept for at least five years after the completion of publications resulting from this support.

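### As the lists are worded, a breast, ovarian or uterine cancer diagnosed without hospital admission or death falls outside the plan's 24-hour reporting rule

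*Combined protocol and SAP*

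**What the plan says.** Everything that governs prompt reporting stands in one section of the combined protocol and SAP, Reporting of Serious and Unexpected Adverse Events.

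- **Trigger.** "Adverse experiences that are both serious and unexpected will be immediately reported by telephone within 24 hr and in writing within 3 days to" the IRB, the GCRC and the Research Subject Advocate.
- **Unexpected events.** "Unanticipated adverse events are breast cancer, ovarian cancer, uterine cancer, intercurrent illness and intercurrent injuries". A separate list of expected events includes breast lumps, abnormal nipple aspirate cytology and abnormal endometrial findings.
- **Serious events.** "Serious adverse events are life threatening drug interaction, death, breach of confidentiality, and hospital admission". No general criterion follows, and nothing marks the four items as examples.
- **Forms.** "A UTMB IRB Adverse Event Report form will be used to report individual serious adverse event". The other form is for repeated events: "For recurring adverse event, an aggregate report form will be generated to provide summary statistics for the study". No deadline is given for it.

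Two other sections say where findings that might be cancer are sent. Clinical Procedures, step 5, deals with an abnormal mammogram at baseline. Risk and Benefit Assessment deals with pathology from an endometrial biopsy after amenorrhea.

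**The concern.** The plan foresees three cancers clearly enough to name them, yet the rule that would send them quickly to the oversight bodies also requires seriousness, and no item on the seriousness list is met by a diagnosis.

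The setting makes a diagnosis without admission plausible. Mammography and MRI are repeated yearly in women who attend as outpatients. Further work-up of an abnormal screening mammogram takes place outside the study and at the woman's own cost (Clinical Procedures, step 5; Cost of Participation).

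Safety is Aim #4. The Nipple fluid aspiration section says that several studies raised a possible stimulatory effect of isoflavones on breast tissue. Risk and Benefit Assessment describes stimulation of breast cancer cells in culture and in mice, and thickening of the uterine lining in some animal studies. The same section says that the breast cancer effect has not so far been found in humans, and that the one available epidemiological study pointed to less endometrial cancer with soy. So the possibility is one the plan raises and has not settled. What is at stake is whether the IRB and the Research Subject Advocate hear promptly of such a case.

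**Working it through.** The plan gives no figure to reproduce. The check applies the reporting rule to the section's own lists and then looks for another route.

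**Step 1: the rule.** Expedited report = serious AND unexpected. Individual IRB form = serious.

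**Step 2: the lists.** The unanticipated list has five items: three cancers, intercurrent illness and intercurrent injury. The serious list has four: life-threatening drug interaction, death, confidentiality breach and hospital admission. They have no item in common. That alone proves nothing, because one list sorts events by type and the other mainly by consequence. The question is whether a given event meets both tests.

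| Event | Unexpected | Serious | 24-hour and 3-day report | Individual IRB form |
|---|---|---|---|---|
| Named cancer, no admission or death | yes | no | not required | not required |
| Named cancer, later admission or death | yes | from the admission or death | from that date | from that date |
| Intercurrent illness, no admission | yes | no | not required | not required |
| Breast lump or abnormal nipple cytology, no admission | no (listed as expected) | no | not required | not required |

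The first row is the gap. The second row shows its limit: admission or death brings the case under the rule, with the clock starting at that event and not at diagnosis. The last row shows that possible early signs of breast cancer do not trigger the expedited report either.

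**Step 3: other routes.**

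- *Aggregate form.* It is for recurring events and has no deadline, so a single cancer does not call for it.
- *Baseline mammogram (Clinical Procedures, step 5).* The woman, a co-investigator and the principal investigator are told, and she is asked to report her follow-up results. The stated consequence is about eligibility: "If the subjects have cancer lesions after further diagnostic tests, they will be excluded from the study". No report to the IRB, GCRC or Research Subject Advocate is stated. Step 13, on the 12-month imaging, adds no reporting instruction.
- *Endometrial biopsy (Risk and Benefit Assessment).* The woman receives the pathology report, and "Reports will also be provided to the Medical Monitor". No deadline and no IRB report is stated.
- *Departure from the Protocol.* This sends certain deviations to the IRB and GCRC. A diagnosis is not a deviation.

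None of these closes the gap.

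**Step 4: how often it could arise.** The planned 200 women followed for 2 years give 200 × 2 = 400 woman-years. The documents give no incidence. As an assumption, take 0.5 to 2 cancers per 1,000 woman-years for the three sites together:

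- low: 400 × 0.0005 = 0.2 cases expected;
- high: 400 × 0.002 = 0.8 cases expected.

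Only cases without prompt admission would be missed or delayed, so the affected number is smaller still. Dropout would lower the 400, and recruiting until 200 women complete 1.5 years would raise it. Neither changes the order of magnitude.

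**The case against.** The best reply is that expectedness and seriousness are separate axes, so the two lists need not overlap. Intercurrent illness works in the same way as cancer: unanticipated by type, reportable once it leads to admission or death. On this view the section is coherent. That part stands. A reader might infer that the sentences contradict each other and that no outside judgement is needed to fault them. The documents do not support this. The text can be followed as written, and calling the result unsatisfactory requires the judgement that a new diagnosis of a named cancer should reach the oversight bodies promptly. That judgement is modest in a trial with a safety aim and these stated uncertainties, but it is a judgement.

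Three further points limit the finding without removing it.

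- The plan never says that unanticipated and unexpected mean the same, nor that the serious list is exhaustive. Both are the natural readings. Without the first, the list of unanticipated events would have no link to the reporting rule.
- The rule sets a minimum. It does not forbid a prompt report of a cancer; it does not require one.
- Most of the section on roles and responsibilities of study personnel was not available for this review. It may describe duties of the Medical Monitor that bear on this point.

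**Conclusion.** The concern holds for one defined case: a breast, ovarian or uterine cancer diagnosed without hospital admission or death. As worded, the section requires neither the 24-hour and 3-day report nor the individual IRB form for it. Where admission follows later, the duty starts then and not at diagnosis.

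A reader might go further and infer that any new cancer escapes prompt reporting. That is too broad, because admission or death brings a cancer under the rule. Nor should the point be read as saying that the product promotes cancer in women, since the plan reports no such finding in humans.

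The practical size is small: fewer than one case expected in the whole trial under the assumed incidence range, and no effect on any efficacy analysis. It still merits correction, because following the rule exactly would leave oversight uninformed of a harm the plan itself names. The conclusion rests on the two readings of the wording given above and on the text that was available.

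**What to change.** In Reporting of Serious and Unexpected Adverse Events, reconcile the unanticipated and serious lists with the reporting rule. State that a new diagnosis of any cancer named there falls under the 24-hour telephone and 3-day written report, and the individual IRB form, from the date the study team learns of it and whether or not the woman is admitted. The same edit can say that unanticipated and unexpected are one category and whether the serious list is complete. If the Medical Monitor's duties already cover this, a cross-reference is enough.

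The cost is about one sentence and at most a few extra reports. The Post-intervention follow-up section describes pill-taking in the past tense. If supplementation has in fact ended, the sponsor should also check that any cancer diagnosed during the study was reported.
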